## 1. Protocol Synopsis

### Observational Synopsis

Protocol Number:	UCDC 5117
Protocol Title:	Comparative Effectiveness of Treatment in Rare Diseases: Liver Transplantation vs. Conservative Management of Urea Cycle Disorders
Study Chair:	[name] [name]
Statistician:	[name]
Consortium:	Urea Cycle Disorders Consortium
Participating Sites:	Children's National Health System The George Washington University National Urea Cycle Disorders Foundation
Activation Date:	March 4, 2016
Sample Size:	Aim 1: 185 (92 with liver transplant, 93 without liver transplant) Aim 2: 32-48 primary caretakers, 25-40 providers Aim 3: 64-48 primary caretakers
Target Enrollment Period:	3 years
Study Design:	Mixed method concurrent study design. Quantitative research methods to address primary outcomes. Qualitative research methods to obtain information on the UCD patient/family experience when making critical treatment decisions
Primary Study Objective:	To study two urea cycle disorder (UCD) patient cohorts, one managed conservatively and the other treated by liver transplantation; comparing survival rate, neurocognitive function and patient-reported quality of life. ( Aim 1 )
Secondary Study Objective:	To examine, through a representative sample of pediatric patient's primary caretakers (typically a parent) and medical providers, including the treating physician and other clinicians on the team, how UCD treatment decisions are made, describing the factors that influence the patient/family's decision to continue conservative management or elect liver transplantation. ( Aim 2 ) To develop a dissemination strategy for study findings of Aim 1 that aligns with the decision-making considerations and process illustrated through Aim 2 and which is responsive to the expressed needs of UCD patients and their primary caretakers. ( Aim 3 )
Study Population and Main Eligibility/Exclusion Criteria:	Aim 1 
 
- Age 18 and under
 
- Diagnosed with the following neonatal-type
 

	
urea cycle disorders: CPSD, OTCD, ASD or ALD, as defined as follows:
 

• Diagnosis of CPS1 deficiency, defined as decreased (less than 20 % of control) CPS1 enzyme activity in liver, and/or an identified pathogenic mutation, and/or hyperammonemia and first-degree relative meets at least one of the criteria for CPS1 deficiency

• Diagnosis of OTC deficiency, defined as the identification of a pathogenic mutation, and/or less than 20% of control of OTC activity in the liver, and/or elevated urinary orotate (greater than 20 <math>\mu</math>M/mM) in a random urine sample or after allopurinol challenge test, and/or hyperammonemia and first-degree relative meets at least one of the criteria for OTC deficiency

• Diagnosis of AS deficiency (Citrullinemia), defined as a greater than or equal to 10-fold elevation of citrulline in plasma, and/or decreased (less than 20% of control) AS enzyme activity in cultured skin fibroblasts or other appropriate tissue, and/or identification of a pathogenic mutation in the AS gene, and/or hyperammonemia and first-degree relative meets at least one of the criteria for AS Deficiency

• Diagnosis of AL deficiency (Argininosuccinic Aciduria, ASA), defined as the presence of argininosuccinic acid in the blood or urine, and/or decreased (less than 20% of control) AL enzyme activity in cultured skin fibroblasts or other appropriate tissue, and/or identification of a pathogenic mutation in the AL gene, and/or hyperammonemia and first-degree relative meets at least one of the criteria for AL Deficiency

 

- Willing to participate in at least 1 neurocognitive assessment and at least 1 quality of life assessment

- Permit access to medical records and medical providers

 
Aims 2 & 3:
 

- Primary caretaker(s) of a patient age 25 and

--	---

	
under who has been diagnosed with either CPSD, OTCD, ASD or ALD (typically a parent, but broadly defined as those individuals who are responsible for making the child's treatment decisions and who also provide the majority of the child's physical and emotional care)
 
 
- Considered, are currently considering, or opted for, liver transplantation as a treatment for UCD.
 
- Willing to participate in a 60-minute semi-structured interview and/or a 60-90 minute focus group discussion
 
 
OR
 
 
- Health care provider (e.g. metabolic disease physician, liver transplant surgeon, gastroenterologist, genetic counselor, or nurse) that participates in treating patients diagnosed with either CPSD, OTCD, ASD or ALD,
 
- Willing to participate in a 60-minute semi-structured interview and/or a 60-90 minute focus group discussion
 

Statistical Considerations	
Aim 1: Covariate-balancing propensity scoring based on the CBPS package in R to create comparable (balanced) groups based on their risk factor (covariate) profile in subjects according to their propensity (probability) to move from conservative management to liver transplantation
 
Aim 2: Thematic content analysis of interview data (collected and coded using QSR International NVivo 10) will form the basis of our interpretation, which will move beyond a typology of participant accounts to look at the relationship between the identified themes
 
Aim 3: Focus group data will also be analyzed using thematic content analysis

Sponsors:	National Institutes of Health (NICHD/NCATS)
Funder:	Patient-Centered Outcomes Research Institute (PCORI)

## 1.1. Overview

Urea cycle disorders (UCD) are genetic disorders caused by the liver's inability to break down ammonia from proteins; ammonia then accumulates and is toxic to the brain. UCD cause brain damage, intellectual, developmental disabilities, and even death. Medical treatment involves special diet low in protein, drugs that help metabolize ammonia and amino acid supplements (conservative management). However, many patients and families choose liver transplantation rather than conservative treatment; both alternatives are effective in reducing or normalizing blood ammonia. While liver transplantation eliminates the ammonia problem, conservative management does so only temporarily and in many patients, blood ammonia can rise during an infection or other stress. The long-term objective of this study is to help patients make decisions about management alternatives (medical vs. liver transplantation) by providing them with scientific information that is currently lacking.

The questions that will be addressed are:

1. What is the disease's risk of mortality and illness in each treatment approach?
2. What can parents expect in terms of the neurocognitive development of their child and his/her school performance?
3. What are the expected effects of each treatment on short-term and long-term quality of life?
4. What factors do primary caretakers (typically parents) consider when making the decision to pursue liver transplantation or continue conservative management for their child with UCD?

This research will have two components. In one, we will use statistical methods to compare survival, illness, psychological testing for IQ, executive function, memory, behaviors, and quality of life among patients that choose conservative management and those who have chosen liver transplantation. Some of this information is already being collected by the Urea Cycle Disorders Consortium (UCDC) in 14 metabolic clinics (11 of them in the US) as part of its longitudinal natural history study. To ensure that the information we analyze is representative of the UCD patient population in the US, we will also obtain data from the Studies of Pediatric Liver Transplantation (SPLIT) registry, which collects information about children who undergo liver transplantation for many different diseases (including UCD), and from the National Urea Cycle Disorders Foundation (NUCDF) a patient advocacy group for patients with UCD.

The qualitative component of this project will consist of individual interviews and focus groups with UCD pediatric patient families and caretakers and medical providers, including treating physicians and other medical staff on the team, to identify the important issues caretakers consider when deciding whether to opt for liver transplantation or continue conservative management.

The NUCDF and its Patient-Powered Research Team (PPRT) collaborated with the clinical investigators to design this research and to ensure that it covers the questions that are most important to patients and their families. The results of this study

will be disseminated to patients and families, doctors and clinical staff so that they receive current, validated information before making a decision about the best treatment choice for the individual patients.

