###### **Historical Data:**

- Eligibility
- Enrollment/demographic information
- Review of past medical records, including:
  - growth charts
  - neurodevelopmental testing
  - neurological evaluation
  - biochemical and diagnostic testing (e.g., ammonia, plasma amino acids, DNA sequencing of UCD genes)

- history of hospitalizations
- medications and other treatments (e.g., dialysis)
- other comorbidities

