## **5.6. Subject Discontinuation**

An intent to treat approach will be used. All data acquired prior to termination for the reasons outlined below will be included in the primary analysis unless patient withdraws consent. Every effort will be made to conduct a final study visit with the participant and participants will be followed clinically until, if applicable, all adverse events resolve.

- Withdrawal of consent
- Withdrawal by the participant
- Withdrawal by the investigator

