## 6. Statistical Considerations

### 6.1. Sample Sizes

**Aim 1.** Of the 185 projected members of the target population, 92 (49.7%) are expected to have received liver transplants and 93 (50.3%) to remain on conservative management. Based on previously published results and characteristics of the UCD patients currently enrolled in our longitudinal study, we expect these groups to be very comparable with respect to UCD severity. As described below, we will use the method of covariate-balanced propensity score matching to create additional groups that are more closely matched on additional severity indicators for the comparative effectiveness analysis. **Table 2** provides a detailed breakdown of the characteristics of study groups.

For **Aims 2 and 3**, we plan to recruit a representative sample of 32-48 patient primary caretakers for participation in semi-structured interviews on their experience making treatment decisions for their child with UCD and an additional 16-48 patient primary caretakers (until a sample of 64-80 is reached) for participation in focus groups to validate information obtained through interviews and to discuss effective dissemination strategies for the evidence-based information obtained through this study.

Table 2. Characteristics of Eligible Transplanted Cases and Comparable Controls										
Group	Total	Type of UCD				Sex M/F	Onset (days)	Peak NH3 (µmol/l)		Surgery Age (mo.)
		CPSD	OTCD	ASD	ALD			# >200, %	Median, IQR	
Transplanted	92	12 (14%)	44 (47%)	22 (24%)	14 (15%)	62/30	2 (1-21)	90 (98%)	958, 938	11.7 (1.5-186)
Conservatively Managed	93	1 (1%)	21 (22%)	37 (39%)	34 (38%)	48/45	3. (1-21)	69 (74%)	403, 781	---

Interview and focus group participants will be stratified by their child's: 1) access to expert care (i.e. yes/no), 2) disease severity (i.e. neonatal onset/post-neonatal onset), and 3) transplant status (pre/no transplant, post-transplant,) (**Tables 3 and 4**). Although not included as an explicit level of stratification, we will also aim to recruit primary caretakers that are diverse in terms of their child's geographic distribution, socioeconomic status, and race/ethnicity.

Table 3. Sample Sizes for Stage 1 Patient Caretaker Interviews				
Disease Severity	Pre/No Transplant			
	Access to Expert Care		Sample Size	
	Yes	No		
Neonatal onset		4-6	4-6	8-12
Post-neonatal onset		4-6	4-6	8-12
Post-Transplant				
Neonatal onset		4-6	4-6	8-12
Post-neonatal onset		4-6	4-6	8-12

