## 6.2. Analysis Plan

For **Aim 1**, we will use covariate balancing propensity scoring based on the CBPS package in R [28] to create comparable (balanced) groups based on their risk factor (covariate) profile in subjects according to their propensity (probability) to move from conservative management to liver transplantation. This approach leads to a model that predicts treatment assignment (conservative vs. liver transplantation) and balances covariates, especially those related to study outcome(s), and offers the best opportunity to simulate RCT results from observational data. From prior experience, many through the UCDC [26,31,32], we know many of the important risk factors, which include neonatal vs. late onset, number of prior hyperammonemic events, event severity in terms of hyperammonemic coma score [2], ammonia and glutamine levels at regularly scheduled clinic visits, and duration from birth to transplant or index date. In addition to these, we will consider comorbidities, organ function, and other laboratory assessments. The CBPS software will help us choose the model that maximizes covariate balance and generate the CBPS for each participant. The next steps will be to order the dataset according to the CBPS. It is useful at this point to select CBPS to cut points to form homogeneous strata to assess the number of subjects with a liver transplant and conservative management per stratum. Those strata where there are

insufficient numbers (mismatches) of conservative treatment or liver transplant subjects will be described, documented and excluded from the primary analysis due to lack of covariate balance. Before conducting model-based analyses for **Aim 1**, we will compare survival times based on the log-rank test in Kaplan-Meier analysis and the difference between mean scores based on t-tests by treatment for neurodevelopment and quality of life within each stratum to evaluate evidence of heterogeneity. Evidence of heterogeneity will provide clues to interactive effects based on UCD severity which will be modeled in regression analyses below by including a cross products term of treatment type with CBPS. Based on these results, we will develop general linear random effects longitudinal regression models in STATA 14

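### The plan poses a question about treatment chosen but groups children by transplant received, with no defined index date and no rule for those who chose transplant but died or deteriorated before surgery

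*Combined protocol and SAP*

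**What the plan says.** - Section 1.1 describes the quantitative comparison as being made "among patients that choose conservative management and those who have chosen liver transplantation". It gives the long-term purpose as helping patients decide between the two options.
- The synopsis and Aim 1 in section 2 describe two cohorts, "one managed conservatively and the other treated by liver transplantation".
- Section 6.1 counts by graft received: "92 (49.7%) are expected to have received liver transplants and 93 (50.3%) to remain on conservative management".
- Section 6.2 builds the propensity score on the "propensity (probability) to move from conservative management to liver transplantation" and lists as a covariate "duration from birth to transplant or index date". The index date is not defined anywhere. The Cox model takes treatment as its predictor. It states no time zero and does not let treatment change over time.
- Section 5.6 says "An intent to treat approach will be used". The sentence stands under subject discontinuation and names no event or date that places a child in a group.
- The historical items in section 4.5 include no date of decision or listing. No Aim 1 text mentions listing, waiting or death before surgery.

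**The concern.** The two ways of grouping differ for one set of children: those whose family chose transplantation but who died or deteriorated before a graft was received. By choice they belong to the transplant option. By receipt they cannot be in the transplanted group.

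A family can choose to pursue transplantation, but it cannot choose to reach surgery alive. The risk of waiting is therefore part of the option the study sets out to describe. Table 2 gives age at surgery as 11.7 months (1.5-186), against onset at 2 days (1-21). There is time for events before surgery, although the documents do not say how much of it follows the decision. The same problem applies to brain injury during the wait, and hence to the neurocognitive comparison.

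**Working it through.** **1. The plan's own split.** 92/185 = 49.7% and 93/185 = 50.3%. Both figures reproduce, and both count by graft received.

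**2. Where could a child go who chose transplant and died before surgery?**

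| Reading | Placement |
|---|---|
| By receipt (Aim 1, 6.1, 6.2) | conservative management |
| By receipt, but not seen as one who remains on conservative management (6.1) | left out |
| Section 5.6 read as intent to treat by choice | transplantation |

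No text selects among these. The first two follow from grouping by receipt.

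**3. Direction.** Counted from the decision, survival under the transplant option is (probability of reaching surgery alive) x (survival after surgery). Grouping by receipt shows only the second factor, which is larger than the product whenever any child dies waiting. Example with 5 assumed waiting deaths, 92 children reaching surgery and 11 deaths after it: 92/97 x 81/92 = 94.8% x 88.0% = 83.5%, against 88.0% by receipt.

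**4. Size, for illustration only.** Inputs:
- Conservative mortality of 28% (power paragraph of 6.2): 26 of 93.
- Transplant mortality of 12%, from the low end of the 88-99% five-year survival in 3.3.2: 11 of 92.
- w waiting deaths and v living waiting children, all counted under conservative management by receipt. Both are assumptions.

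By choice, conservative mortality = (26 - w)/(93 - w - v) and transplant mortality = (11 + w)/(92 + w + v).

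| w | v | Conservative | Transplant | Gap (points) |
|---|---|---|---|---|
| 0 | 0 | 26/93 = 28.0% | 11/92 = 12.0% | 16.0 |
| 3 | 0 | 23/90 = 25.6% | 14/95 = 14.7% | 10.8 |
| 3 | 6 | 23/84 = 27.4% | 14/101 = 13.9% | 13.5 |
| 5 | 0 | 21/88 = 23.9% | 16/97 = 16.5% | 7.4 |
| 5 | 10 | 21/78 = 26.9% | 16/107 = 15.0% | 12.0 |
| 5 | 18 | 21/70 = 30.0% | 16/115 = 13.9% | 16.1 |
| 8 | 0 | 18/85 = 21.2% | 19/100 = 19.0% | 2.2 |
| 8 | 16 | 18/69 = 26.1% | 19/116 = 16.4% | 9.7 |

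The rows with v = 0 assume that nobody is alive and waiting, and so exaggerate the effect. In these crude proportions, transplant mortality rises on regrouping whenever w/(w + v) exceeds 12.0%. Conservative mortality falls only when w/(w + v) exceeds 28.0%. With 5 deaths and 18 living (5/23 = 21.7%), the transplant figure is still understated by receipt, but the gap hardly changes.

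If waiting deaths drop out instead, the 26/93 stays as it is and only the transplant side changes. With w = 5 and v = 0 the gap is 28.0 - 16.5 = 11.5 points.

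**5. Would the usual survival repair be enough?** Treating transplant as time-varying from the surgery date removes the guaranteed survival before surgery. Deaths while waiting would still be charged to conservative management. Answering 1.1 needs the decision or listing date.

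**The case against.** The strongest reply is that the operative text is consistent. Aim 1, 6.1 and 6.2 all group by treatment received, and only a plain-language overview speaks of choice. A child who is waiting is in fact managed conservatively, so under a by-receipt aim that time and that death belong there. This stands as far as it goes: the by-receipt comparison is legitimate and should be kept. But 1.1 is where the question for families is stated, and by-receipt results alone do not answer it.

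A reader might infer three stronger things that the documents do not support.
- *That a waiting death is counted under conservative management.* No rule says so. The child might be left out, or placed with transplantation if 5.6 is read by choice.
- *That these children cannot be identified later.* The record review in 4.5 is open-ended, families are interviewed, dates are to be noted carefully, and 4.1 requires access to records and providers. The point is that nothing obliges anyone to collect the date.
- *That the mortality gap is inflated by a calculable amount.* The counts are unknown, living waiting children pull the other way, and the 28% has no stated horizon while the 12% is a five-year figure.

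The routes of entry also limit the effect. New participants must be able to undergo assessment, and SPLIT is described as covering children who undergo transplantation. Waiting deaths could therefore enter mainly through longitudinal-study data or later follow-up.

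**Conclusion.** The concern holds in a limited form. The stated question and the grouping differ, the index date is undefined, and no rule covers children who chose transplantation and died or deteriorated before surgery. If the plan is followed by receipt, the transplanted group contains only children who reached surgery, so its survival is flattered relative to the option families actually choose. That direction holds for survival counted from the decision whenever any child dies waiting.

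The size cannot be derived from the documents. Where the illustration moves two living children for each death, the gap falls from 16.0 points to 13.5, 12.0 or 9.7 for 3, 5 or 8 waiting deaths. Other assumed counts give other answers, including almost no change. These figures show sensitivity and are not estimates.

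**What to change.** 1. Add to 4.5 the date on which transplantation was chosen or the child was listed. Request the same date as a de-identified item from the longitudinal-study data: its participants are not recruited here (4.3), so a chart-review field alone may not reach them.
2. In 6.2, set one time zero for both groups, for example diagnosis or matched index dates. A start date for the transplant option alone would create new guaranteed survival time. Add a survival analysis in which a child enters the transplant option at the decision or listing date, as a time-varying exposure. Deaths after that date and before surgery count there, as does the follow-up of living children still waiting.
3. Report the by-receipt analysis beside it, with transplant as a time-varying exposure from surgery.
4. Where a child died untransplanted and the decision date is unknown, report bounds with the death assigned each way. The surgery date cannot stand in, because these children have none.
5. Reconcile the wording of 1.1, 5.6, the objective and 6.1, and define the assignment event and the index date.

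The cost is one extra data item, some missing dates in older records and one extra analysis. The request to the longitudinal study should go out early.

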## 2. Specific Aims (Hypothesis and Objectives)

This study will compare the outcomes of liver transplantation vs. medical treatment in patients with UCD for survival, neurocognitive status, and quality of life. The specific aims are:

**Aim 1:** To study two urea cycle disorder (UCD) patient cohorts, one managed conservatively and the other treated by liver transplantation, comparing survival rate, neurocognitive function and patient-reported quality of life.

**Aim 2:** To examine, through a representative sample of pediatric patient primary caretakers and medical providers, including the treating physician and other clinicians on the team, how UCD treatment decisions are made, describing the factors that influence a primary caretaker's decision to continue conservative management or proceed to a liver transplant.

**Aim 3:** To develop a dissemination strategy for study findings of **Aim 1** that aligns with the decision-making process illustrated through **Aim 2** and which is responsive to the expressed needs of UCD patients and their primary caretakers.

This study's goal is to fill a critical needs gap by providing objective evidence of risk and benefit that will serve as a solid foundation for the decision-making process. The current decision-making process relies largely on subjective judgment. The study results and dissemination will provide patients and families with evidence-based information that is currently lacking on the treatment alternatives (conservative management vs. liver transplantation), including answers to the following questions: 1. What is the disease-specific risk of mortality and morbidity in the two approaches? 2. What outcomes can patients expect in terms of cognitive development and/or other developmental milestones? 3. What are the pros and cons in terms of quality of life considerations? The study will provide qualitative information on the decision-making process that caretakers undertake when choosing between these treatment alternatives so that dissemination efforts around study results can be designed to align with this process and better address caretakers' expressed needs and concerns.

